# DOCUMENT VERSION CONTROL

Version Number	Date	Comments/Changes	
0.1	16 January 2019	First Draft	
0.2	23 October 2019	Second Draft, updated per final Sept 20 th 2019 version of CSP	
0.3	2 March 2020	Third Draft, updated per January 2020 consensus meeting	
0.4	13 April 2020	Fourth Draft, updated per March 2020 consensus meeting	
0.5	20 May 2020	Fifth Draft, updated per May 2020 consensus meeting	
0.6	18 June 2020	Sixth draft, updated per comments	
0.7	01 July 2020	Seventh draft, updated per comments	
1.0	10 July 2020	Finalize	
1.1	09 June 2021	Changes: reference to protocol amendment in section 1 updated; demographics age category updated; duplicate subjects section 3.3 added; mITT population added for primary and key secondary end points, as well as sensitivity analyses for primary end points; convention for negative GSP values added; subgroup analyses added; AE text added about date imputation algorithm, local site reactions, figures, and overall summary table; formatting updates; update to TLF list; text added to Section 13	
2.0	30 July 2021	Changes: Section 8.3.7 update to PP analyses – PP is a completers population, so no multiple imputation is needed; Section 8.2.2 - analysis center pooling updated to add further combinations should models not converge; Sections 8.3.1 and 8.3.2 - method for combining p-values for site poolability added and method for selecting overall p-values for mixed effects model added; update to titles in TLF list	

Version: 2.0 Page 2 of 74

# **LIST OF ABBREVIATIONS**

AE	Adverse event	
ANCOVA	Analysis of Covariance	
ATC	Anatomic Therapeutic Chemical	
BBI-4000	Sofpironium bromide	
CBI	Control Based Imputation	
СМН	Cochran-Mantel-Haenszel	
CSR	Clinical study report	
CRF	Case report form	
DLQI	Dermatology Life Quality Index	
eCOA	Electronic clinical outcome assessment	
eCRF	Electronic case report form	
EDC	Electronic data capture	
EOT	End of Treatment	
GSP	Gravimetric sweat production	
HDSM-Ax	Hyperhidrosis Disease Severity Measure-Axillary	
ICH	International Council on Harmonisation	
ITT	Intent-to-Treat	
MAR	Missing at Random	
MedDRA	Medical Dictionary for Regulatory Activities	
mITT	Modified intent-to-treat	
MMRM	Mixed model repeated measures	
NMAR	Not Missing at Random	
PGI-C	Patient Global Impression of Change	
PGI-S	Patient Global Impression of Severity	
PP	Per-protocol	
REML	Restricted maximum likelihood	
SAE	Serious adverse event	
SD	Standard deviation	
SI	Systeme International	
TEAE	Treatment-emergent adverse event	
WHO	World Health Organization	

Version: 2.0 Page 6 of 74

ı	IQT	ΩF		ΓΕΧΤ	TΛ	RI	FC
L	.101	UE	114-			\DL	.EJ

Table	8-2	Summary of Sensitivity Analyses of the Co-Primary Efficacy	
		Endpoints	. 33

Version: 2.0 Page 7 of 74

#### 1. PURPOSE OF THE ANALYSES

This statistical analysis plan (SAP) contains detailed information to aid in the implementation of the statistical analyses and reporting of the study data for use in the clinical study report (CSR) for study BBI-4000-CL-301. This SAP is being written with due consideration of the recommendations outlined in the most recent International Conference on Harmonisation (ICH) E9 Guideline, entitled Guidance for Industry: Statistical Principles for Clinical Trials, and the most recent ICH E3 Guideline, entitled Guidance for Industry: Structure and Content of Clinical Study Reports.

This SAP describes the data sets that will be used for analysis, as well as subject characteristics, efficacy, safety, and clinician-reported and patient-reported perception of disease severity and improvement parameters. The details of the specific statistical methods stated in the protocol will be provided and any changes from the protocol-specified analyses will be documented in the SAP prior to database lock. If additional analyses are required to supplement the planned analyses described in this SAP after the database lock, they may be completed and will be described in the CSR. Table, figure, and listing specifications are provided as an attachment in a separate document. This SAP amendment to Amendment 1.1 dated June 09, 2021 is based on Amendment 3 of the BBI-4000-CL-301 protocol dated August 6, 2020 (Original September 20, 2019).

Version: 2.0 Page 8 of 74

### 2. PROTOCOL SUMMARY

## 2.1 Study Objectives

The purpose of this Phase 3 study is to assess the safety, local tolerability, and efficacy of sofpironium bromide gel, 15% when applied topically to subjects with primary axillary hyperhidrosis.

#### Primary:

- To evaluate the safety and local tolerability of sofpironium bromide gel, 15% when applied topically to subjects with primary axillary hyperhidrosis.
- To evaluate the effect of sofpironium bromide gel, 15% on hyperhidrosis disease severity as it relates to sweat production, patient-reported outcomes, and quality of life self-assessments.

## 2.2 Study Endpoints

#### 2.2.1 Primary Endpoints

There are 2 co-primary efficacy endpoints:

- 1. The proportion of subjects achieving at least a 2-point improvement in Hyperhidrosis Disease Severity Measurement-Axillary, 7-item (HDSM-Ax-7) scale score from baseline to end of treatment (EOT).
- 2. The change in gravimetric sweat production (GSP) from baseline to EOT.

### 2.2.2 Secondary Endpoints

The following secondary efficacy endpoints will be analyzed:

- The proportion of subjects achieving at least a 1-point improvement in the HDSM-Ax-7 scale score from baseline to EOT.
- The proportion of subjects achieving at least a 2-point improvement in the HDSM-Ax-7 scale score from baseline to EOT and achieving at least a 70% reduction in GSP from baseline to EOT.
- The proportion of subjects achieving at least a 1-point improvement in the HDSM-Ax-7 scale score from baseline to EOT and achieving at least a 50% reduction in GSP from baseline to EOT.

Version: 2.0 Page 9 of 74

# 2.2.3 Exploratory Efficacy Endpoints

Exploratory efficacy endpoints to be analyzed include the following:

- The proportion of subjects achieving at least a 1-point improvement in the HDSM-Ax-7 scale score from baseline to Days 8, 15, 22, 29, 36, 41, 42, 43 (EOT), and 57.
- The proportion of subjects achieving at least a 1-point improvement in the HDSM-Ax, 11-Item (HDSM-Ax-11) scale score from baseline to Days 8, 15, 22, 29, 36, 41, 42, 43 (EOT), and 57.
- The proportion of subjects achieving at least a 2-point improvement in the HDSM-Ax-7 scale score from baseline to Days 8, 15, 22, 29, 36, 41, 42, 43 (EOT), and 57.
- The proportion of subjects achieving at least a 2-point improvement in the HDSM-Ax-11 scale score from baseline to Days 8, 15, 22, 29, 36, 41, 42, 43 (EOT), and 57.
- The proportion of subjects achieving at least a 1-point improvement in the HDSM-Ax Question 4 score from baseline to Days 8, 15, 22, 29, 36, 41, 42, 43 (EOT), and 57.
- The proportion of subjects achieving at least a 2-point improvement in the HDSM-Ax Question 4 score from baseline to Days 8, 15, 22, 29, 36, 41, 42, 43 (EOT), and 57.
- The proportion of subjects achieving at least a 1-point improvement in the HDSM-Ax Question 5 score from baseline to Days 8, 15, 22, 29, 36, 41, 42, 43 (EOT), and 57.
- The proportion of subjects achieving at least a 2-point improvement in the HDSM-Ax Question 5 score from baseline to Days 8, 15, 22, 29, 36, 41, 42, 43 (EOT), and 57.
- Change in Patient Global Impression of Severity (PGI-S) from baseline to Days 8, 15, 22, 29, 36, 41, 42, 43 (EOT), and 57.
- Patient Global Impression of Change (PGI-C) score on Day 43 (EOT).
- The proportion of subjects achieving at least a 2-point improvement in the HDSM-Ax-11 scale score from baseline to EOT and achieving at least a 70% reduction in GSP from baseline to EOT.
- The proportion of subjects achieving at least a 1-point improvement in the HDSM-Ax-11 scale score from baseline to EOT and achieving at least a 50% reduction in GSP from baseline to EOT.
- The proportion of subjects achieving at least a 2-point improvement in the HDSM-Ax-7 scale score and achieving at least a 70% reduction in GSP from baseline to Days 8, 15, 22, 29, 36, 41, 42, 43, EOT, and Day 57.

Version: 2.0 Page 10 of 74

- The proportion of subjects achieving at least a 2-point improvement in the HDSM-Ax-11 scale score and achieving at least a 70% reduction in GSP from baseline to Days 8, 15, 22, 29, 36, 41, 42, 43, EOT, and Day 57.
- The proportion of subjects achieving at least a 1-point improvement in the HDSM-Ax-7 scale score and achieving at least a 50% reduction in GSP from baseline to Days 8, 15, 22, 29, 36, 41, 42, 43, EOT, and Day 57.
- The proportion of subjects achieving at least a 1-point improvement in the HDSM-Ax-11 scale score and achieving at least a 50% reduction in GSP from baseline to Days 8, 15, 22, 29, 36, 41, 42, 43, EOT, and Day 57.
- Change in HDSM-Ax-7 scale score from baseline to Days 8, 15, 22, 29, 36, 41, 42, 43 (EOT), and 57 as a continuous measure.
- Change in HDSM-Ax-11 scale score from baseline to Days 8, 15, 22, 29, 36, 41, 42, 43 (EOT), and 57 as a continuous measure.
- The proportion of subjects achieving at least a 70% reduction in GSP from baseline to Days 8, 15, 22, 29, 36, 41, 42, 43, EOT, and Day 57.
- The proportion of subjects achieving at least a 50% reduction in GSP from baseline to Days 8, 15, 22, 29, 36, 41, 42, 43, EOT, and Day 57.
- The rank-based GSP change from baseline to Days 8, 15, 22, 29, 36, 41, 42, 43, EOT, and Day 57.
- The absolute GSP change from baseline to Days 8, 15, 22, 29, 36, 41, 42, 43, EOT, and Day 57.
- The percent change from baseline in GSP from baseline to Days 8, 15, 22, 29, 36, 41, 42, 43, EOT, and Day 57.
- The change in the Dermatology Life Quality Index (DLQI) (axilla) from baseline to Day 15 and Day 43 (EOT).

## 2.2.4 Safety Endpoints

Safety assessments of interest are local tolerability assessments, adverse events, laboratory evaluations, and vital signs.

# 2.3 Overall Study Design and Plan

This is a multicenter, randomized, double-blinded, vehicle-controlled, Phase 3 study to evaluate the safety and efficacy of topically applied sofpironium bromide gel, 15% in subjects with primary axillary hyperhidrosis.

Approximately 350 subjects, at up to approximately 45 clinical sites in the United States, will be randomized to receive either sofpironium bromide gel, 15%, or vehicle gel (placebo) in a balanced 1:1 ratio in order to obtain approximately 300 evaluable subjects at the end of study.

Version: 2.0 Page 11 of 74

Subjects will apply the investigational product (either sofpironium bromide gel, 15%, or vehicle gel) once daily at bedtime to each axilla for 42 consecutive days.

Patient-reported outcomes HDSM-Ax, Patient Global Impression of Severity (PGI-S), Patient Global Impression of Change (PGI-C; EOT only), and Dermatology Life Quality Index (DLQI), as well as Investigator-reported GSP, will be recorded during the study at predefined timepoints. Vital signs and local tolerability assessments will be collected at Visits 4 through 9 and Visits 12 (EOT) and 13. Adverse events will be collected at each post-Screening visit. Blood and urine samples will be collected and analyzed at Screening and Visit 12 (EOT) for routine hematology, chemistry, and urinalysis parameters. Additionally, a urine pregnancy test for females of child-bearing potential will be collected and analyzed at Visits 1, 4, 8, and 12.

A total of 13 scheduled visits will take place over approximately 11 to 15 weeks, depending on when the Baseline Visit (treatment) is scheduled after the three (3) screening period visits: initial screening, GSP1, and GSP2.

## 2.4 Study Population

Subjects aged ≥9 years with a diagnosis of primary axillary hyperhidrosis.

### 2.5 Treatment Regimens

Either sofpironium bromide gel, 15% or vehicle gel (placebo) topically applied to the axillae once daily at bedtime for 42 consecutive days.

## 2.6 Sample Size Determination

Sample size estimation was performed for the co-primary efficacy endpoints based on the results of a Phase 2b study (BBI-4000-CL-203):

- HDSM-Ax-7 responder analysis: 2-point improvement response rates of 29.8% and 53.7% were assumed for the vehicle and sofpironium bromide gel, 15% arms, respectively. The power is 0.95 with 116 subject per arm and a total of 232 subjects.
- GSP: using rank-transformed GSP data for change from baseline to EOT, a
  difference of 16.6 in mean ranks between vehicle and sofpironium bromide gel,
  15% arms, with a pooled standard deviation of approximately 39.5, was used for
  this purpose. Normal approximation yielded a sample size estimate of 296
  subjects for the study, 148 in each arm, in order to achieve 0.95 power for the
  GSP co-primary endpoint.

A chi-square test for the HDSM-Ax-7 endpoint and a two-sample t-test for the GSP endpoint were used to estimate the above sample size and power for each endpoint. With approximately 300 evaluable subjects, the overall study power to demonstrate a statistically significant treatment effect (two-sided p < 0.05) for both co-primary

Version: 2.0 Page 12 of 74

endpoints simultaneously is greater than 0.90 (with greater than 0.95 power for each of HDSM-Ax-7 and GSP). It is estimated that 350 total subjects will need to be randomized (in a 1:1 allocation) for there to be 300 subjects completing the co-primary efficacy assessments (approximately 15% drop-out rate).

Additionally, sample size estimation was also performed using non-rank-transformed GSP data. An expected mean treatment difference of 73 mg with a pooled standard deviation of approximately 170 was used for this purpose. This yielded a reduced sample size estimate compared with the target of 300 subjects completing the co-primary efficacy assessments in order to achieve 0.95 power for GSP, further indicating that our sample size estimations are conservative.

Version: 2.0 Page 13 of 74

#### 3. GENERAL ANALYSIS AND REPORTING CONVENTIONS

## 3.1 Reporting Conventions

The following is a list of general analysis and reporting conventions to be applied to this study, unless otherwise specified.

All data displays (tables, listings, and figures) will have a header showing the sponsor company name, protocol number, page number, and display status (i.e. "DRAFT" or "FINAL"), as well as a footer indicating file name and run date/time. Summary tables and data listings will be summarized by treatment, as appropriate. All data collected perprotocol will be listed. Derived variables may also be listed.

Categorical variables will be summarized using counts (n) and percentages (%) and will be presented in the form "n (xx.x)." If a count is 0, no percentage will be shown. If a percentage is 100%, 100% will be shown with no decimal place. To ensure completeness, summaries for categorical variables will include all categories, even if no subjects had a response in a particular category. Unless otherwise specified, the denominator for each percentage will be based on the number of subjects with available data in the population being summarized. If there are missing values, counts will be shown but will not be included in percentage calculations.

Continuous variables will be summarized using mean, standard deviation (SD), minimum, maximum, median, and number of subjects. The mean and median will be reported to an additional level of precision than the original observation in its rawest form (i.e. on the eCRF), and the SD and other measures of variability (e.g. standard error) will be reported to two additional levels of precision than the original observations. The minimum and maximum will be the same precision as the original data. In general, any calculated values, such as those due to unit conversion, will be rounded to the same number of decimal places as the original data.

Unless otherwise specified, all statistical tests will be 2-sided using  $\alpha$ =0.05. Estimates and confidence intervals will be reported to 1 more decimal than the original data. P-values will be reported to 4 decimal places. P-values less than 0.0001 will be displayed as "<0.0001"; p-values greater than 0.9999 will be displayed as ">0.9999".

Summary tables and data listings:

- No preliminary rounding will be performed; rounding will only occur after analysis.
- Data from subjects excluded from an analysis population will be presented in the data listings but will not be included in the calculation of summary statistics, where applicable.

Version: 2.0 Page 14 of 74

- Data from each subject will be separated by a blank line. Within a data listing, if a descriptive item appears line after line (e.g., repetition of a subject number, date, visit, etc.), only the first occurrence will be displayed (e.g., in Listing of Vital Signs, subject number, date and visit will only be displayed on first row when presenting all parameters collected at same visit). Repetition of actual results or outcomes (e.g., Adverse Events (AEs), lab results, vital sign values, etc.) will not be collapsed.
- Data listings will be sorted by site, subject, treatment, and week and/or time of assessment, unless otherwise noted.
- When change from baseline is calculated, baseline is the last observation obtained prior to dosing of the study drug unless otherwise specified.

Mock tables and data listings will be provided as attachments to this analysis plan. Minor changes to the mocks after formal SAP approval will not necessitate re-approval unless changes to the text of the SAP are required.

All statistical deliverables will be produced, validated, and reviewed for accuracy/consistency in accordance with Rho, Inc. standard operating procedures and the processes described in the statistical validation plan.

SAS® (SAS Institute, Cary, North Carolina) statistical software, version 9.4 or later, will be used for all analyses. Adverse Events and Medical History will be coded using the most recent version of the Medical Dictionary for Regulatory Activities (MedDRA). Concomitant medications will be coded using the latest version of the World Health Organization (WHO) Drug and Anatomical-Therapeutic-Chemical (ATC) classification and preferred term.

#### 3.2 Standard Calculations

Unless otherwise noted, baseline is defined as the last observed data value prior to the receiving of the first application of treatment for treated subjects, and the last observed data value prior to the randomization date for randomized subjects who were not treated. The baseline derivation can include unscheduled visits.

Study day will be determined as:

- The assessment/event date minus the date of first dose of gel, if the assessment/event date is prior to the date of first dose of gel; and
- The assessment/event date minus the date of first dose of gel + 1, if the assessment/event date is on or after the date of first dose of gel. For example, Day 1 is defined as the date of the first dose of gel.

Version: 2.0 Page 15 of 74

Note that if the subject is randomized but not treated then the randomization date will be Day 1 for Schedule of Event purposes. Change from baseline will be calculated as the post-baseline data value minus the baseline value. Percent change from baseline will be calculated as the change from baseline divided by the baseline value, multiplied by 100.

Unless otherwise noted, values reported as greater than or less than some quantifiable limit (e.g., "< 2.0") will be summarized as such in summary tables and figures. However, analysis will be performed using the numeric equivalent, e.g. "<2.0" will be analyzed as 2.0. Summary tables and figures will be footnoted when such practices occur.

Partial or missing dates used in calculations of duration may be imputed with logic similar to that of Adverse Events (Section 9.2).

#### 3.3 Duplicate Subjects

During the course of the BBI-4000-CL-301 study, some subjects were identified as having registered for study participation at more than one site and/or in the second Phase 3 pivotal study (BBI-4000-CL-302); these subjects are said to be duplicate subjects. Duplicate subjects are identified as such in the individual study subject listings.

For analyses using the Intent-to-treat (ITT) Population or the Safety Population: (a) duplicate subjects with repeat registrations in the same study will have each registration analyzed as a different study subject with his/her unique subject ID; (b) For subjects who registered to both BBI-4000-CL-301 and BBI-4000-CL-302, the registrations will remain in each study as subjects for the respective study.

Duplicate subjects will be removed from the modified ITT (mITT) Population (See Section 4) for the co-primary efficacy endpoints, secondary efficacy endpoints and sensitivity analyses of the co-primary efficacy endpoints.

Version: 2.0 Page 16 of 74

#### 4. ANALYSIS POPULATIONS

Identification of the subjects to be included in each analysis population will be determined and finalized prior to database lock and unblinding. Subjects will be classified into the Safety, Intent-to-Treat (ITT), Per-Protocol (PP), and modified Intent-to-Treat (mITT) populations according to the following definitions:

### **Safety Population**

The Safety Population will include all subjects randomized in the study who received study drug, either vehicle or sofpironium bromide, 15%, at least once. Subjects will be analyzed according to the treatment actually received. If a subject receives any sofpironium bromide gel, 15%, the subject will be analyzed in the sofpironium bromide gel group. Otherwise the subject will be included in the vehicle group.

### **Intent-to-Treat (ITT) Population**

The ITT Population will include all subjects who were randomized. Subjects will be analyzed according to the treatment group to which they were randomized, regardless of post-randomization protocol deviations, including no treatment or wrong treatment received.

#### Per-Protocol (PP) Population

The PP Population will be a subset of the mITT Population and will include subjects who meet the following criteria:

- Meets all inclusion/exclusion criteria
- Has not taken or applied any interfering concomitant medications
- Completed the following visits:
  - Visit 2 GSP 1, and the required GSP data collection
  - o Visit 3 GSP 2, and the required GSP data collection
  - Visit 4 (Day 1) Re-screening/Baseline GSP 3 and HDSM-Ax, and the required GSP and HDSM-Ax data collection
  - $\circ$  Visit 10 (GSP 4) Day 41 ( $\pm$  2 days), and the required GSP data collection
  - $\circ$  Visit 11 (GSP 5) Day 42 ( $\pm$  2 days), and the required GSP data collection
  - Visit 12 (GSP 6) Day 43 (± 2 days) and HDSM-Ax, and the required GSP and HDSM-Ax data collection

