## 10.1.2 Per-Protocol Population

The PP Population will be a subset of the ITT Population and will include subjects who meet the following criteria:

- Meets all inclusion/exclusion criteria
- Has not taken or applied any interfering concomitant medications
- Completed the following visits:
  - Visit 2 GSP 1, and the required GSP data collection
  - o Visit 3 GSP 2, and the required GSP data collection
  - Visit 4 (Day 1) Re-screening/Baseline GSP 3 and HDSM-Ax, and the required GSP and HDSM-Ax data collection
  - $\circ$  Visit 10 (GSP 4) Day 41 ( $\pm$  2 days), and the required GSP data collection
  - $\circ$  Visit 11 (GSP 5) Day 42 ( $\pm$  2 days), and the required GSP data collection
  - Visit 12 (GSP 6) Day 43 (± 2 days) and HDSM-Ax, and the required GSP and HDSM-Ax data collection

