## Modified Intent-to-Treat (mITT) Population

The mITT Population will be a subset of the ITT Population and excludes subjects with duplicate enrollments either within BBI-4000-CL-301 or across BBI-4000-CL-301 and BBI-BL-4000-CL-302 (see Section 3.3). All other subjects will be analyzed according to the treatment group to which they were randomized, regardless of post-randomization protocol deviations, including no treatment or wrong treatment received.

Version: 2.0 Page 17 of 74

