### 5.2 Protocol Violations

Major protocol violations will be summarized by treatment group for the Safety Population. Major protocol violations may include, but will not be limited to the following:

- Not meeting eligibility criteria;
- Randomization error;
- Received no protocol treatment or wrong treatment;
- Non-compliance with study drug dosing;
- On-study administration of a prohibited medication;
- Unauthorized changes to protocol procedure that could potentially affect subject safety or are a flagrant deviation of protocol defined procedures.

All major protocol violations will be determined and appropriately categorized prior to database lock and prior to breaking the blind of the treatment group assignments. The number and percentage of subjects with any major protocol violations as well as the number and percentage of subjects with violations within each category will presented. A per subject listing will be provided for all protocol violations, major or minor, for the Safety Population.

Version: 2.0 Page 18 of 74

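### The per-protocol set has no criterion for receiving the randomised gel, so untreated or wrongly treated subjects who completed the required visits stay in it

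*SAP*

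**What the plan says.** - **SAP Section 4, PP definition.** The set starts from mITT: "The PP Population will be a subset of the mITT Population and will include subjects who meet the following criteria". The criteria are eligibility, "Has not taken or applied any interfering concomitant medications", and completion of Visits 2, 3, 4, 10, 11 and 12 with the data due at each. The Visit 12 entry, for example, ends "and HDSM-Ax, and the required GSP and HDSM-Ax data collection".
- **Protocol Section 10.1.2.** The same three criteria, beginning with "Meets all inclusion/exclusion criteria", applied to ITT instead of mITT.
- **SAP Section 4, mITT definition.** Only duplicate enrolments are removed. Everyone else is kept "regardless of post-randomization protocol deviations, including no treatment or wrong treatment received".
- **SAP Section 5.2.** "Major protocol violations may include, but will not be limited to the following": six examples follow, among them "Received no protocol treatment or wrong treatment" and "Non-compliance with study drug dosing". Categories are fixed before lock and unblinding. Their stated use is a table and a listing for the Safety Population.
- **SAP Section 7.** Exposure is a percentage of expected doses, summarised descriptively with no cut-off.
- **SAP Section 8.3.7.** The co-primary analyses are repeated in PP as exploratory, and the secondary and exploratory endpoints are also analysed there. The section describes PP as made up of completers and uses observed data only.

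**The concern.** A reader of the study report will usually take a per-protocol result as the effect in subjects treated as the protocol required. Here, one interfering medication removes a subject, while never having had the assigned gel does not. The SAP plans to identify such subjects before the blind is broken but does not use that information to form the set. At stake is how the PP results for both co-primary and all three secondary endpoints are read. Any untreated or wrongly treated subjects in the set would be expected to pull the PP difference towards zero.

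**Working it through.** **1. Listed examples of major violations against the PP criteria.**

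| Example in SAP 5.2 | Reached by a PP criterion? |
|---|---|
| Eligibility not met | Yes, directly |
| Randomisation error | No |
| No treatment or wrong treatment | No |
| Dosing non-compliance | No |
| Prohibited medication on study | Yes, as far as it counts as interfering |
| Unauthorised procedure change | No |

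The visit criterion removes subjects in the four uncovered rows only if they also missed a required visit or its data.

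**2. Search for another rule that closes the gap.**
- The parent population does not: mITT keeps these subjects explicitly.
- SAP Section 5.1 reports reasons for exclusion from PP but adds none.
- Protocol Section 7.4 says that a non-compliant subject may be discontinued, after contact with the Medical Monitor. This is permissive.
- Inclusion criterion 5 (Protocol Section 4.2) concerns the ability to follow procedures, not what the subject later did.
- SAP Section 7 sets no threshold.

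So a subject who received no gel or the wrong gel, and who meets the three criteria, remains in PP.

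**3. Whether the planned exposure measure could serve as a compliance rule.** Under SAP Section 7, expected doses = 2 × (last dose date − first dose date + 1), and received doses = expected − recorded missed doses. Take a subject who applied every dose on Days 1 to 10, then stopped, with no missed dose recorded:
- expected = 2 × 10 = 20; received = 20 − 0 = 20; exposure = 20/20 = 100%;
- against the planned 42 days: 2 × 42 = 84 doses, so 20/84 = 23.8%.

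The measure as defined can show full exposure for a subject who stopped early. A threshold would need the planned period as its denominator.

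**4. Size, as an illustration.** The plan gives no PP effect and no rate for these violations, so there is no stated figure to reproduce. Inputs from Protocol Section 10.5 and SAP Section 2.6: vehicle 29.8%, active 53.7%, difference 53.7 − 29.8 = 23.9 points. Let f be the assumed share affected, with subjects analysed under their randomised arm.
- A share f of active-arm PP subjects respond at the vehicle rate: D = (1 − f) × 53.7 + f × 29.8 − 29.8 = (1 − f) × 23.9.
- A share f of each arm received the other gel: D = (1 − 2f) × 23.9.

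| f (assumed) | Active arm only | Both arms swapped |
|---|---|---|
| 2% | 0.98 × 23.9 = 23.4 | 0.96 × 23.9 = 22.9 |
| 5% | 0.95 × 23.9 = 22.7 | 0.90 × 23.9 = 21.5 |
| 10% | 0.90 × 23.9 = 21.5 | 0.80 × 23.9 = 19.1 |

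Partial non-compliance is not modelled, because the documents give no relation between missed doses and response.

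**The case against.** The strongest reply is that the SAP does not present PP as an adherent population. Section 8.3.7 calls it a set of completers and makes its co-primary analysis exploratory, and no success criterion or testing step depends on it. The case is also uncommon by design. The subject must complete six specified visits, dosing is queried at Visits 5 to 12, pumps are weighed at dispensing and return, and containers are matched to IRT-assigned numbers. All of that stands, and it keeps the point small. It does not close the gap, because none of these checks feeds into PP membership.

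Four stronger readings are tempting, and the documents do not support them.
- A reader might infer that the SAP firmly classes every such case as a major violation. Section 5.2 says only that major violations may include these categories, and it gives dosing non-compliance no cut-off.
- A reader might infer that wrongly treated subjects are analysed in PP under their randomised arm. That is plausible, since mITT works that way, but Section 4 does not say so for PP. Analysis as treated would remove the dilution from swapped gels.
- A reader might infer that such subjects exist in the trial. The documents show only that the rule would admit them.
- A reader might conclude that agreement between ITT and PP carries almost no information. PP still differs from ITT on eligibility, medication, duplicate enrolment and completion, and the illustrated shifts are modest.

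Excluding on adherence after randomisation also has a cost: if tolerability drives adherence, the exclusion can select differently in the two arms.

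**Conclusion.** The gap is real, and closing it is a cheap improvement to an exploratory analysis. A subject who received no gel or the wrong gel but met the eligibility, medication and visit criteria stays in PP. Under the assumption that 5% of active-arm PP subjects respond like vehicle, the difference drops by 23.9 − 22.7 = 1.2 points; at 10% it drops by 23.9 − 21.5 = 2.4 points. These shares are assumptions. The results also rest on the planning response rates and on analysis by randomised arm. The ITT conclusion, the type I error rate and the testing sequence are unaffected. The conclusion is firm for receipt of the randomised gel. For dosing compliance it is conditional, because the plan defines no level that would count as non-compliant.

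**What to change.** 1. Add to SAP Section 4 that PP excludes subjects classified before unblinding under Section 5.2 as "Received no protocol treatment or wrong treatment", including randomisation errors that led to the wrong gel. Make this classification for all randomised subjects: the Section 5.2 table covers the Safety Population, which by definition omits anyone who never received study drug.
2. Record the departure from Protocol Section 10.1.2 in SAP Section 13.
3. Exclude for "Non-compliance with study drug dosing" only if the sponsor sets a numeric threshold before unblinding, measured against the planned treatment period and not from first to last dose. Otherwise, label the set in tables and report as completers and do not describe it as adherent.

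The cost is a short SAP edit that uses a classification already planned. The downsides are a slightly smaller exploratory population and, if the compliance rule is added, possible selection related to tolerability.
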